12.2 Calculation or derivation of efficacy variable(s)

12.2.1 Differential cell count (absolute and percentage neutrophils)

The Sputum samples: waking sample, the 2 hour collection and the 1 to 2 hour post-dose samples will be derived and analysed separately.

The mean of the values from Visit 1a, 1b and 2 will be used as baseline for differential cell count. The change from baseline to treatment (mean of the values at Visits 3a, 3b and 4, or Visit 4 only, where appropriate) will be used as outcome variable(s). The other differential counts will be reported for completeness.

12.2.2 Weight of 24 hour sputum collection

The value from Visit 2 will be used as baseline. The change from baseline to end of treatment (Visit 4) will be the primary analysis.

12.2.3 Lung function tests

The values from Visit 2 will be used as baseline for lung function parameters. If the Visit 2 value is missing, the Visit 1 value will be used as baseline instead. The change from baseline to treatment will be used as outcome variable(s).

Change from baseline to Visit 4 will be the primary analysis.

12.2.4 Calculation and derivation of patient reported outcome variables

12.2.4.1 Bronkotest[®] diary card data

Bronkotest[®] data will be summarised as the mean of each period: Baseline period – the mean of the last 7 days prior to start of treatment, and Treatment period - the mean of the last 7 days. The change from baseline to treatment will be used as the outcome variable.

N.B. Morning and evening PEF recordings will be calculated separately.

12.2.4.2 St George's Respiratory Questionnaire (SGRQ-C)

The SGRQ-C will be summarized as 3 different domain scores (symptom, activity and impacts) and a total score given for each patient and visit. Each questionnaire response will be scored using weights according to the SGRQ-C manual. Questions not applicable for some patients will be given the weight zero. The domain scores will be calculated by dividing the summed weights by the maximum possible score for that component and expressing it as a percentage. The minimal clinically important difference (MID) has been defined as a change in score of ≥ 4 units in the total score and impact score. The primary outcome variable for SGRQ-C will be the change in mean total score from baseline (Visit 2) to Visit 4 (using the last available value). The domain scores will be handled in the same way.

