3. STUDY OBJECTIVES

3.1 Primary objective

The primary objective is to investigate whether AZD9668 shows evidence of efficacy in bronchiectasis patients by investigation of:

- Absolute and percentage neutrophil cell count in the sputum
- Signs and symptoms of bronchiectasis (including effects on quality of life)

The associated primary outcome variables can be found in Table 1.

Table 1 Primary outcome variables

Outcome Variables	Description
Absolute and percentage neutrophil cell count in sputum	Absolute cell count will be performed and sputum cytospin slides will be produced for assessment of differential cell count
Bronkotest © diary card	The Bronkotest © diary card will be completed by patients from enrolment until follow up visit, to capture signs and symptoms of their bronchiectasis
24 hour sputum collection weight	Patients will be asked to collect sputum for a 24 hour period on 2 occasions during the study
St George's Respiratory Questionnaire	The quality of life questionnaire "St George's Respiratory Questionnaire for COPD patients" (SGRQ-C) will be completed pre treatment and at the end of the treatment period
Lung function tests	The following lung function tests will be assessed at clinic visits 1, 2, 4 and 5. SVC (slow vital capacity), FEV1 (forced expiratory volume in 1 second), FVC (forced vital capacity), forced expiratory flow between 25 and 75% of forced vital capacity (FEF25-75)

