ⁱ After collecting the waking sputum sample in one pot, patients should collect another sample (of at least 1 to 2 g sputum) in another pot, over a maximum of 2 hours. Immediately after finishing collection of the 2 hour sample, all sputum samples should be taken directly to the clinic or dispatched directly to the local sputum processing lab (dependent on the clinic appointment time and/or patient's preference).

^j Details of all analytes measured in these spontaneous sputum samples can be found in Table 4 .

^k Plasma and serum samples will be collected. See Section 7.6.2.

^l If the patient discontinues after randomisation they should be asked to attend for Visit 5.

^m The aliquot for the quantitative sputum culture will be taken from the waking sample at Visit 2.

Table 4 Spontaneous sputum sample summary

Timing of sample	Visit 1	Visit 1a	Visit 1b	Visit 2 (pre dose)	Visit 2a	Visit 3	Visit 3a	Visit 3b	Visit 4 (pre dose)	Visit 4 (1-2 hours post dose)	Visit 5
Analysis											
Cytospin production		✓ ^b	✓ ^b	✓ ^b			✓ ^b	✓ ^b	✓ ^b	✓	
AZD9668 sputum concentration				✓ ^b					✓ ^b	✓	
Aliquots for pharmacodynamic marker (including inflammatory and mucus hyper-secretion markers)		✓ ^b	✓ ^b	✓ ^b			✓ ^b	✓ ^b	✓ ^b	✓ ^a	
Quantitative sputum culture				✓ ^c							✓ ^c

^a Aliquot for NE activity only

^b Waking sputum sample and 2 hour sputum collection

^c Waking sample only

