5.4.2 Procedures for discontinuation of a patient from the study

A patient that discontinues will always be asked about the reason(s) for discontinuation and the presence of any adverse events. If possible, they will be seen and assessed by an investigator(s). Adverse events will be followed up (See Sections 7.3.3 and 7.3.4); diary cards and study drug should be returned by the patient.

If a patient discontinues they should be asked to attend the follow up visit (Visit 5).

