7.2.1 Follow-up procedures

Investigators should refer to the study plan in Table 3 for a detailed list of study procedures and assessments to be performed at the follow up visit (Visit 5). The following assessments will be performed and recorded in the pCRF at this visit:

- Physical examination

- Safety blood samples (Haematology and Clinical Chemistry) and a mid stream urine sample for urinalysis
- Lung function tests (FEV₁, SVC, FVC, FEF25-75)
- Vital signs (Blood pressure and pulse)
- A 12 lead ECG
- Concomitant medications
- Adverse event questioning

In addition, the patients will return their completed Bronkotest[®] diary card and their spontaneous sputum collection for quantitative bacterial culture as detailed in Section 7.3.9.1.

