7.4.2.2 St George’s Respiratory Questionnaire (SGRQ-C)

The St George’s Respiratory Questionnaire (SGRQ-C) will be completed by patients at Visits 2 and 4 (as outlined in Table 3). The questionnaire takes approximately 10 minutes to answer the questions.

Questionnaire

The St George’s Respiratory Questionnaire (SGRQ) has been developed to measure the impact of respiratory disease on health status. The SGRQ-C is a shorter version of the SGRQ specially adapted for COPD (Meguro et al 2007). The SGRQ-C contains 3 domains: Symptoms (distress due to respiratory symptoms), Activity (disturbance of physical activity) and Impacts (overall impact on daily life and well being). The UK English version is attached in Appendix E, and is the version translated into other local languages as required.

Administration of PRO questionnaires

The SGRQ-C is paper based and answers should be completed, by hand, by the patient at the relevant clinic visits (refer to Table 3).

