13.1 Description of analysis sets

There will be one Efficacy Analysis Set which will be used for all analysis; this set will comprise all patients randomised into the study, who have received at least one dose of study medication and have at least one piece of evaluable data. This dataset should be the same as the safety analysis set, this will be confirmed at the Blind Review.

The blinded data will be investigated further at the Blind Review and if appropriate a Per Protocol analysis set may be defined. The Per Protocol analysis set would consist of all patients in the Efficacy Analysis Set, except for those who had a major protocol deviation (as defined at the Blind Review).

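### The SGRQ-C last-value rule can only carry the baseline forward as zero change, or do nothing, because the questionnaire is given only at Visits 2 and 4

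*Protocol*

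**What the plan says.** SGRQ-C is one of several primary variables (Protocol synopsis; section 3.1, Table 1). The relevant statements are:

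- **Outcome (section 12.2.4.2).** The primary SGRQ-C variable is the "change in mean total score from baseline (Visit 2) to Visit 4 (using the last available value"). For the domains: "The domain scores will be handled in the same way".
- **Schedule (sections 7.4.2.2 and 3.1).** The questionnaire "will be completed by patients at Visits 2 and 4 (as outlined in Table 3"). Table 1 agrees: it "will be completed pre treatment and at the end of the treatment period". Table 3 marks no other visit.
- **Discontinuation (section 5.4.2).** "If a patient discontinues they should be asked to attend the follow up visit (Visit 5"). A footnote to Table 3 in section 4.1 repeats this: "If the patient discontinues after randomisation they should be asked to attend for Visit 5".
- **Content of Visit 5 (section 7.2.1).** The list introduced by "The following assessments will be performed and recorded in the pCRF at this visit" does not include the SGRQ-C, and neither does the Visit 5 column of Table 3.
- **Analysis set (section 13.1).** The Efficacy Analysis Set keeps randomised patients who "have received at least one dose of study medication and have at least one piece of evaluable data", so a patient who stops early stays in.
- **Model (synopsis).** Primary variables are compared by analysis of variance with treatment and country or centre as factors and baseline as covariate, with a two-sided 90% confidence interval.

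**The concern.** A last-value rule needs at least one post-baseline measurement before the endpoint visit. Here there is none. When Visit 4 is missing, the only SGRQ-C value the schedule can supply is the Visit 2 score, so subtracting baseline from it gives 0 by construction.

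That zero would enter the model as if it had been observed. The treatment estimate is then a mixture of real changes and constructed zeros, in proportions set by dropout in each arm. The zeros also add apparent sample size and reduce apparent spread, so the interval is narrower than the Visit 4 data justify.

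Loss of Visit 4 need not be balanced. Section 5.4.1 lists QTc, liver, haemolysis, platelet and compliance grounds for stopping, some of which could differ by arm. Replacing withdrawals (section 6.2) does not remove the problem: withdrawals for adverse events are not replaced, and a replaced patient still meets the definition of the Efficacy Analysis Set.

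**Working it through.** **Plan's own figure.** The protocol states no effect size, SD or power for SGRQ-C. Its sample size reasoning (section 13.3) concerns sputum neutrophils, so there is no figure to reproduce on this point.

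**Inputs from the protocol.** 20 patients per group (section 13.3); two-sided 90% interval (section 13.2); minimal important difference of 4 units (section 12.2.4.2).

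**Assumed inputs.** Dropout per arm of 5% to 25%; SD of change of 10 units; patients who drop out would have had the same mean Day 28 change as those who stay. The comparison is of mean changes without covariate adjustment, for simplicity.

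**Step 1: what the rule returns.** Scheduled SGRQ-C values are Visit 2 and Visit 4 only. With Visit 4 missing, change = Visit 2 - Visit 2 = 0.

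**Step 2: expected difference under the literal reading.** With dropout d_A (active) and d_P (placebo) and true mean changes m_A and m_P:

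expected difference = (1 - d_A) × m_A - (1 - d_P) × m_P

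Negative values favour active.

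| True changes (active, placebo) | Dropout (active, placebo) | Calculation | Result | Truth |
|---|---|---|---|---|
| -4, 0 | 10%, 10% | 0.90 × (-4) - 0 | -3.6 | -4 |
| -4, 0 | 20%, 20% | 0.80 × (-4) - 0 | -3.2 | -4 |
| -6, -2 | 20%, 5% | -4.8 - (-1.9) | -2.9 | -4 |
| -6, -2 | 5%, 20% | -5.7 - (-1.6) | -4.1 | -4 |
| -4, -4 | 5%, 25% | -3.8 - (-3.0) | -0.8 | 0 |

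Equal dropout multiplies the difference by (1 - d). Unequal dropout can shrink it, enlarge it, or create one where none exists. The last row corresponds to 1 versus 5 losses among 20 per arm.

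**Step 3: standard error.** With the zeros included, the variance of change in an arm with mean m and SD s is (1 - d)(s² + m²) - [(1 - d)m]². Take s = 10, true changes -4 and 0, and d = 20%:

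- Active: 0.8 × 116 - 3.2² = 92.8 - 10.24 = 82.56. Placebo: 0.8 × 100 = 80.
- SE with zeros: √(82.56/20 + 80/20) = 2.85.
- SE with observed cases, 16 per arm: 10 × √(2/16) = 3.54.
- Ratio: 2.85/3.54 = 0.81.

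At d = 10% the two values are 3.01 and 3.33, a ratio of 0.90. The standard error therefore falls by roughly (1 - d) as well.

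**Step 4: power.** Estimate and standard error shrink together, so the test statistic hardly moves. At d = 20% and SD 10, power for a 4-unit difference at two-sided 0.10 is 30.1% with the zeros and 30.4% with observed cases. The damage is to the estimate and its interval.

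**The case against.** The strongest reply is that section 12.2.4.2 never says that baseline is carried forward. If the last available value means the last post-baseline value, nothing can be carried and the patient has no SGRQ-C change. Section 13 promises a full SAP before unblinding, where the meaning could be settled. It can also be said that the study is declared exploratory, that SGRQ-C is one of many primary variables, that it did not drive the sample size, and that 28-day dropout may be low.

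The point about meaning stands: zero scoring is the literal reading, not an established intention. It does not rescue the wording, because the other reading leaves the phrase without effect. Nor is this detail left to the SAP, since the protocol itself states the rule. The remaining points bear on severity.

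A reader might infer more than the documents support:

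- *Every early discontinuation scores zero.* Only a patient with a Visit 2 score and no Visit 4 score does. Without a Visit 2 score there is no change at all. A completer with a missing Visit 4 form is affected in the same way.
- *The difference is always pulled toward zero.* That holds under equal dropout. The -4.1 and -0.8 rows above show otherwise when dropout is unequal.
- *Visit 5 should also gain a sputum sample and a 24-hour sputum weight.* That is a separate design preference. The protocol states no faulty carry-forward rule for those variables, and the additions would need local sample processing, further collection pots and changes to the visit tables.

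**Conclusion.** The concern holds. Given the schedule, the phrase either imputes exactly zero change on a primary variable or does nothing, and neither is a usable rule. On the literal reading, equal dropout of 10% to 20% turns a 4-unit difference into 3.6 to 3.2, with a standard error about 10% to 20% below that of the observed cases. A 5% versus 25% imbalance with a 4-unit fall in both arms produces a false 0.8 units, one fifth of the minimal important difference.

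These sizes rest on assumed dropout rates and on dropouts changing like completers. If stopping treatment itself reduces benefit, the difference among all randomised patients is already below 4, and the shortfall attributable to the rule is smaller.

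Severity is moderate. A reader might infer that the flaw threatens the study's conclusion, but the study is exploratory, power is little affected, and no success rule rests on SGRQ-C alone.

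**What to change.** In section 12.2.4.2, delete the parenthesis on the last available value and state that a Visit 2 score is never used as a post-baseline value. Analyse observed Visit 4 scores, total and domains, in the baseline-adjusted model already planned. With data missing at random, the expected difference then stays at its true value. This is a wording change with no effect on visits or procedures. The price is that patients without a Visit 4 questionnaire contribute no SGRQ-C change, and the interval is correspondingly wider.

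Optionally, collect the SGRQ-C when Visit 5 serves as the discontinuation visit and record the days since last dose, for a sensitivity analysis only. Section 7.4.2.2 puts the questionnaire at about 10 minutes. This part would alter Table 3 and need an amendment under section 9.5. Some of the scores would be obtained off treatment and should be labelled as such.

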12.3 Calculation or derivation of pharmacokinetic variables

The pharmacokinetic (PK) analyses will be performed at (or under the guidance of) AstraZeneca R&D [REDACTED]. The actual sampling times will be used in the PK calculations. PK parameters will be determined using standard non-compartmental methods. The following PK parameters will be determined: Concentration of AZD9668 in plasma and sputum.

12.4 Calculation or derivation of pharmacodynamic variable(s)

The Sputum samples: waking sample, the 2 hour collection and the 1 to 2 hour post dose samples will be derived and analysed separately.

The mean of the values, pre treatment (Visit 1a and/or Visit 1b and/or Visit 2, as applicable) will be used as baseline for inflammatory markers (blood, sputum and urine). The values recorded at the end of the treatment (Visits 3a and/or Visit 3b and/or Visit 4 as applicable) will be investigated for variability and if acceptable the change from baseline to the mean of these values will be used as the endpoint.

12.4.1 Calculation or derivation of the relationship between pharmacokinetic and pharmacodynamic variables

Relationship between AZD9668 sputum concentration and the effect on NE activity will be presented graphically (subject to a validated assay being available). If appropriate concentration-effect relationships will be explored.

12.5 Calculation or derivation of pharmacogenetic variables

Details can be found in Appendix D.

12.6 Calculation or derivation of health economics variables (Not Applicable)

13. STATISTICAL METHODS AND SAMPLE SIZE DETERMINATION BY ASTRAZENECA OR DELEGATE

A comprehensive SAP will be prepared before database lock and unblinding of the data in order to avoid any potential bias due to knowledge of the treatment received.

Statistical analyses will be performed by the [REDACTED] AstraZeneca, using SAS[®] version 8.1 and, where appropriate, additional validated software. These analyses will be performed in accordance with this Statistical Analysis Plan (SAP), which will detail analyses to be performed and summaries to be produced for the Clinical Study Report (CSR).

Pharmacokinetic, pharmacodynamic and pharmacogenetic analyses will be carried out by AstraZeneca.

13.1 Description of analysis sets

There will be one Efficacy Analysis Set which will be used for all analysis; this set will comprise all patients randomised into the study, who have received at least one dose of study medication and have at least one piece of evaluable data. This dataset should be the same as the safety analysis set, this will be confirmed at the Blind Review.

The blinded data will be investigated further at the Blind Review and if appropriate a Per Protocol analysis set may be defined. The Per Protocol analysis set would consist of all patients in the Efficacy Analysis Set, except for those who had a major protocol deviation (as defined at the Blind Review).

13.1.1 Analysis of Safety population

All patients who received at least 1 dose of Investigational Product (IP) and for whom post-dose data are available will be included in the safety population. Throughout the safety results sections, erroneously treated patients (eg, those randomised to treatment A but actually given treatment B) will be accounted for in the actual treatment group.

13.2 Methods of statistical analyses

The outcome variables from the Bronkotest[®] diary card, lung function, sputum and blood collections will be compared between AZD9668 and placebo using an analysis of variance model with fixed factors treatment and country (or centre) and using baseline as a covariate. As the study is exploratory in nature, a p-value of <0.1 will be considered significant. A 2-sided 90% confidence interval will be constructed for the treatment difference and p-values given. For variables with a skewed distribution, data may be log-transformed prior to analysis or a non-parametric test (Wilcoxon rank sum) used instead.

The sputum samples: waking sample, the 2 hour collection and the 1 to 2 hour post dose samples will be analysed separately, with the 2 hour sample being the primary sample for data analysis.

All data will be listed, and will be summarised and plotted as appropriate, further details of the output to be produced will be contained in the SAP.

Withdrawal rates will be compared graphically between AZD9668 and placebo and may be investigated further.

Adverse events will be analysed by means of descriptive statistics and qualitative analysis. AEs will be listed for each patient and summarised by System Organ Class and preferred term assigned to event by using MedDRA.

Concomitant medications will be classified according to the WHO Drug Dictionary, the ATC system and the CPMP route of administration dictionary. All concomitant medications reported at entry and recorded during the study will be listed.

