- To investigate the effect of AZD9668 on urine desmosine (marker of tissue degradation)

The Exploratory Objectives are:

- To investigate the effect of AZD9668 on other markers of tissue degradation
- To investigate the effect of AZD9668 on markers of mucus hyper-secretion
- To collect samples for possible retrospective pharmacogenetics analysis to investigate the influence of genotype on pharmacokinetics (and pharmacodynamic response where appropriate). This will not form part of the Clinical Study Report (CSR).

Study design

This is a randomised, double-blind placebo-controlled, parallel group study in patients with bronchiectasis. Forty patients will be randomised to treatment at a ratio of 1:1 (AZD9668:placebo). Patients who complete the study, will be required to attend 10 visits, some of which may be undertaken in their own home.

There will be an optional pharmacogenetics element to collect samples that may be used for the possible retrospective analysis to investigate the influence of genotype on pharmacokinetics (and pharmacodynamic response, where appropriate). Further details can be found in Appendix D.

Target patient population

Male and female (non child bearing potential) patients between 18 and 80 years, with a clinical diagnosis of idiopathic or post-infective bronchiectasis as confirmed by historical high resolution computerised tomography (HRCT) or bronchogram.

Investigational product, dosage and mode of administration

AZD9668 will be administered orally as a dose of 60 mg (2 x 30mg tablets) twice a day (b.i.d) for 28 days.

Comparator, dosage and mode of administration

Matching placebo tablets will be administered orally, two tablets, twice a day (b.i.d) for 28 days

Duration of treatment

Treatment will continue for 28 days unless any of the discontinuation criteria are met.

Outcome variable(s):

Primary variables

- Sputum neutrophils:
 - Absolute and percentage neutrophil cell count
- Signs and symptoms of bronchiectasis:
 - Bronkotest[®] diary card data
 - Weight of 24 hour sputum collection (pre-treatment versus end of treatment)
 - Quality of life as assessed by St George's Respiratory Questionnaire
 - Lung function tests: (Forced expiratory volume in one second [FEV₁], Slow vital capacity [SVC], Forced vital capacity [FVC], forced expiratory flow between 25 and 75% of forced vital capacity [FEF₂₅₋₇₅])

Secondary variables

- Safety variables

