 - vital signs, ECG, haematology, clinical chemistry, urinalysis, sputum culture, reported adverse events.
- Pharmacokinetic variables
 - AZD9668 concentration in plasma and sputum
- Pharmacodynamic variables
 - NE activity in sputum (subject to the availability of validated assay)

- Other inflammatory markers in sputum, including, but not limited to (and subject to the availability of validated assays): TNF- α , IL-8, LTB-4, IL-6, IL-1 β , RANTES, MCP-1
- Blood inflammatory markers, including, but not limited to (and subject to the availability of validated assays): differential cell count [absolute and percentage neutrophils], TNF- α , IL-8, high sensitivity CRP, Amyloid-A, IL-6, IL-1 β
- Urine desmosine (marker of tissue degradation)
- **Exploratory variables**
 - Plasma desmosine and sputum hydroxyproline (markers of tissue degradation)
 - MUC5AC in sputum (marker of sputum hyper secretion)

Subject to the availability of validated assays.

- Retrospective pharmacogenetic analysis to investigate the influence of genotype on the pharmacokinetics of AZD9668 (and pharmacodynamic response where appropriate). Further details can be found in Appendix D.

Statistical methods

The primary outcome variables will be compared between AZD9668 and placebo using an analysis of variance model with fixed factors treatment and country (or centre) and using baseline as a covariate. As the study is exploratory in nature, a p-value of <0.1 will be considered significant. A 2-sided 90% confidence interval will be constructed for the treatment difference and p-values given. For variables with a skewed distribution, data may be log-transformed prior to analysis or a non-parametric test (Wilcoxon rank sum) used instead. The primary outcome variable analyses will be carried out on the Efficacy Analysis Set.

All other data will be summarised and listed.

There will not be an interim analysis for this study.

Pharmacokinetic analyses will be carried out by, or under the guidance of, the [REDACTED] group within AstraZeneca

TABLE OF CONTENTS	PAGE
TITLE PAGE	1
PROTOCOL SYNOPSIS.....	2
TABLE OF CONTENTS.....	6
LIST OF ABBREVIATIONS AND DEFINITION OF TERMS	11
1. IMPORTANT MEDICAL PROCEDURES TO BE FOLLOWED BY THE INVESTIGATOR	15
1.1 Medical emergencies and AstraZeneca contacts	15
1.2 Overdose	16
1.3 Pregnancy.....	16
1.3.1 Maternal exposure.....	16
1.3.2 Paternal exposure	17
2. INTRODUCTION	17
2.1 Background.....	17
2.2 Research hypothesis.....	18

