13.3 Determination of sample size

The sample size for this study was selected to be consistent with the research hypothesis as described in Section 2.2.

This study is exploratory and as such the sample size in this study has not been based on obtaining power to detect specific effects. There is not adequate data to do such a powering. However, assuming that the variability is such (SD=1 on logged data) that we would not miss

(80% power) a 50% decrease in neutrophil numbers in the sputum, a sample size of 40 patients (20 per group) would be sufficient.

Details relating to the optional pharmacogenetics component can be found in Appendix D.

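### The Wilcoxon rank sum option for skewed variables drops the covariate adjustment and loses power to a rank method that keeps baseline, with no gain in type I error control

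*Protocol*

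**What the plan says.** Section 13.2 fixes an analysis of variance with treatment and country (or centre) as factors and baseline as covariate. It states that "A 2-sided 90% confidence interval will be constructed for the treatment difference and p-values given" and sets the threshold: "As the study is exploratory in nature, a p-value of <0.1 will be considered significant". For skewed data it allows two departures: "For variables with a skewed distribution, data may be log-transformed prior to analysis or a non-parametric test (Wilcoxon rank sum) used instead". The synopsis, under Statistical methods, gives the same choice for the primary outcome variables. Neither place says when to prefer one route over the other, and the rank sum test is the only non-parametric method named.

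The outcome that would enter the test is a change. For sputum neutrophils, section 12.2.1 takes baseline as the mean of Visits 1a, 1b and 2 and defines the outcome as "The change from baseline to treatment (mean of the values at Visits 3a, 3b and 4, or Visit 4 only, where appropriate"). Section 13.3 discusses sample size for the same variable on the log scale, "assuming that the variability is such (SD=1 on logged data"), with 20 patients per group.

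**The concern.** The two permitted routes are not equivalent. Log transformation keeps the whole model: baseline, country and the interval for the adjusted difference. The plain rank sum test keeps only the treatment comparison.

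Subtracting baseline is not the same as adjusting for it. On the log scale with equal variances, the change has variance 2(1−ρ) and the baseline-adjusted outcome has variance 1−ρ². Their ratio is (1+ρ)/2, so the adjusted analysis is the more precise whenever the correlation ρ is below 1. On the raw scale subtraction does worse, because changes in skewed counts depend heavily on how high each patient started.

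At stake is the chance of detecting a real effect in a 40-patient trial, for variables that include sputum neutrophils, 24 hour sputum weight and the inflammatory markers. A rank method that keeps baseline uses data already collected.

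**Working it through.** **Inputs.** From section 13.3: 20 per arm, SD 1 on logged data, a 50% decrease. From section 13.2: two-sided 0.10. Assumed, because the protocol does not give them: natural logs, SD 1 applying to the log on-treatment value and to log baseline, and baseline-outcome correlation ρ of 0.3, 0.5, 0.7 or 0.8. The effect is ln 2 = 0.693.

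**The plan's own figure.** n per arm = 2(z₁+z₂)²·SD²/δ².
- One-sided 0.10, 80% power: 2(1.282+0.842)²/0.693² ≈ 18.8, so 19 per arm. This agrees with the protocol's 20.
- Two-sided 0.10: 2(1.645+0.842)²/0.693² ≈ 25.7, so 26 per arm. Power with 20 per arm is 69 to 71%.

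That mismatch is a separate point. The comparisons below all use two-sided 0.10.

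**Closed-form check on the log scale.** The noncentrality is 0.693/(SD·√(2/20)). For Wilcoxon it is multiplied by √0.955, the test's efficiency under normality. The critical value is 1.645.
- ρ = 0.3, ANCOVA: SD = √0.91 = 0.954, noncentrality 2.298, power Φ(0.653) = 74%. Wilcoxon on change: SD = √1.4 = 1.183, noncentrality 1.853 × 0.977 = 1.810, power Φ(0.165) = 57%. Gap about 17 points.
- ρ = 0.8, ANCOVA: SD = 0.600, noncentrality 3.653, power Φ(2.008) = 98%. Wilcoxon: SD = 0.632, noncentrality 3.466 × 0.977 = 3.387, power Φ(1.742) = 96%. Gap about 2 points.

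**Simulation.** Lognormal data, 6000 trials per setting, no country effect, power in %:

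| Analysis | ρ=0.3 | 0.5 | 0.7 | 0.8 |
|---|---|---|---|---|
| Wilcoxon, raw change | 43 | 51 | 68 | 81 |
| Rank ANCOVA, raw change | 60 | 67 | 80 | 91 |
| Rank ANCOVA, on-treatment value | 70 | 76 | 88 | 95 |
| Wilcoxon, log change | 55 | 68 | 86 | 95 |
| Log-scale ANCOVA | 73 | 80 | 91 | 97 |

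Differences in points, at ρ = 0.3/0.5/0.7/0.8:
- Same raw change, baseline added by rank ANCOVA: 17/16/12/10.
- Wilcoxon on raw change against rank ANCOVA on the on-treatment value: 27/25/20/14. At ρ = 0.3 this splits into 60−43 = 17 from adding baseline and 70−60 = 10 from changing the outcome; at 0.8 into 10 and 4.
- Wilcoxon on log change against log-scale ANCOVA: 18/12/5/2.

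The Monte Carlo standard error of each power is at most √(0.25/6000), or 0.65 points, so gaps move by a point or more between runs. Separate runs put the first gap at 10 or 11 at ρ = 0.8 and the log-scale gap at 15 to 18 at ρ = 0.3. A repeat with 40,000 trials per setting reproduced every power above to within about 1 point.

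Type I error was about 9 to 11% for every method. An assumed country shift of 0.5 SD, with 40% of patients in one country, changed the loss by about 1 to 4 points. With heavy-tailed data the gain on raw change was about 3 to 20 points, and with ordinal data about 3 to 16.

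**The case against.** The strongest case against is that the protocol states nothing false. Both routes are optional; log transformation is named first and keeps the full model; section 13.3 already treats neutrophil numbers as logged; and section 13 promises a SAP before database lock and unblinding that could settle the choice. Validity is not threatened: randomisation is unstratified, so omitting country does not bias the test, and the study is declared exploratory. All of this stands and limits the weight of the point. It does not remove it, because the protocol does not leave the non-parametric method open: it names an unadjusted one.

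Three stronger readings are tempting and not supported.
- A reader might infer a fixed cost of 20 to 28 points from dropping baseline and country. A gap of that size arises only when Wilcoxon on raw change is set against an analysis of a different outcome or scale, and at the lower assumed correlations. Against parametric ANCOVA on the same untransformed scale, the loss is only 13/10/3/1 points at ρ = 0.3/0.5/0.7/0.8.
- A reader might infer that the baseline data are thrown away. They are still subtracted. Nor does the averaging over three baseline visits apply everywhere: 24 hour sputum weight and the blood markers each have one pre-treatment collection.
- A reader might infer that no interval would be available. An unadjusted Hodges-Lehmann interval can accompany the test; only the adjusted one is lost, and section 13.2 does not use the word adjusted.

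Exactly lognormal data also favour the log model. The heavy-tailed and ordinal results answer that in part: the advantage of adjusting persists but varies widely.

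**Conclusion.** The point holds as one of efficiency. Where the Wilcoxon option is used, the plan gives up power that a baseline-adjusted rank analysis would keep, for no gain in error control. On the protocol's own raw-change outcome the loss is about 17 points at a correlation of 0.3, falling to 10 or 11 at 0.8. Against rank ANCOVA on the on-treatment value it is about 27 down to 14 points, part of which comes from the change of outcome and scale. On log change, against log-scale ANCOVA, it is about 18 down to 2. Baseline accounts for the covariate loss; country contributes little. The figures rest on the assumed correlations, on natural logs and on SD 1 applying to log values at both times. If log transformation is chosen instead, the loss does not arise.

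**What to change.** In section 13.2 and the synopsis:
- Make log-scale ANCOVA, with treatment, country and log baseline, the stated route for skewed positive variables (counts, sputum weight, markers), reported with its 90% interval.
- Where a rank method is still needed, replace the plain Wilcoxon test with a baseline-adjusted rank analysis of covariance (Quade type) on the on-treatment value.
- Keep plain Wilcoxon as a sensitivity analysis, with an unadjusted Hodges-Lehmann interval if wanted.
- Do not pair a rank p-value with an interval from a log model judged inadequate, and do not rank within country if the strata are small.

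The cost is a sentence in each place and a few lines of code, with no extra patients or samples. The small downside is that the rank ANCOVA p-value has no directly matching interval.
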